5. SAFETY

Safety assessment will be evaluated through AEs and clinical hematology and chemistry laboratory tests. Safety analyses will be based on the safety population and presented by the treatment actually received.

5.1. Adverse Events

All adverse events whether serious or non-serious, will be reported from the time a signed and dated informed consent form (ICF) is obtained until 30 days after the last dose of study treatment, until the subject withdraws consent for study participation, or until the subject starts subsequent antimyeloma therapy, whichever occurs first. AEs will be recorded in standard medical terminology and graded according to the National Cancer Institute Common Terminology Criteria for Adverse Events (NCI-CTCAE), Version 4.03. For AE reporting, the verbatim term used in the CRF by investigators to identify adverse events will be coded using the latest version of Medical Dictionary for Regulatory Activities (MedDRA) coding dictionary.

Unless otherwise specified, at each level (e.g., system organ class and/or preferred term) of subject summarization in reporting the incidence of the AE, a subject is counted once if one or more events were recorded. For summarizing new onset events, all event records of the same preferred term from the same subject are to be linked by the onset date and the end date. If an event is followed by another event of the same preferred term with an onset date (or date/time) the same as or 1 day (or 1 minute if applicable) after the end date (or date/time) of the previous record and any features of the adverse event (i.e.: toxicity grades/seriousness/action taken) are different between these two records, these 2 records should be linked together and considered as one event. A Grade 5 event will be linked to previous event of the same preferred term if the onset date of grade 5 record is the same or one day after the end date of previous record.

All summaries of AEs will be based on treatment-emergent adverse events (TEAEs), which are defined as any AE that occurs after start of the first study treatment through 30 days after the last study treatment; or the day prior to start of subsequent antimyeloma therapy, whichever is earlier; or any AE that is considered drug-related (very likely, probably, or possibly related) regardless of the start date of the event; or any AE that is present at baseline but worsens in toxicity grade or is subsequently considered drug-related by the investigator.

The incidence of TEAEs will be summarized overall, by MedDRA system organ class (SOC) and preferred term, by toxicity grade, and by relationship, to study treatment administration. Specifically, the following AE summaries will be presented by treatment group.

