8.4. Subsequent Therapies

After discontinuation of study therapy subjects should continue disease evaluations per the Time and Events Schedule until confirmed PD or until the cut-off date for the final CSR analysis, whichever is earlier. Subsequent anti-myeloma therapy cannot be started before disease progression is established per the IMWG criteria (Section 9.2.1.1, Response Categories) and confirmed by the sponsor. This sponsor confirmation is no longer required after the cut-off for the final CSR analysis.

After PD (and sponsor confirmation when required), choice of subsequent therapy is at the discretion of the investigator. Subjects randomized to Arm A (Rd) may have the option to receive daratumumab provided by the sponsor (in any subsequent line of therapy) if recommended by the

investigator. Eligibility for and administration of daratumumab including safety management (eg, infusion-related reactions and HBV monitoring) must be in accordance with local prescribing information and local regulations. For these subjects, daratumumab should not be added to an ongoing subsequent therapy regimen until the subject has progressed on that regimen. Subjects in Arm A (Rd) who receive daratumumab after PD through the sponsor will remain in the long-term survival follow-up phase of the study. Serious adverse events must be reported for these subjects until 30 days after daratumumab is discontinued. Second primary malignancies will continue to be reported until end of study.

All subsequent therapy for multiple myeloma (including start and end date, best response, and date of progression to the subsequent therapy) should be documented in the appropriate section of the eCRF, including during long-term survival follow-up.

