12.3. Procedures

12.3.1. All Adverse Events

All adverse events and special reporting situations, whether serious or non-serious, will be reported from the time a signed and dated ICF is obtained until 30 days after the last dose of study treatment until the start of the long-term survival follow-up, unless the subject withdraws consent for study participation, or starts subsequent anti-myeloma therapy. For subjects still receiving study treatment after the final CSR analysis and until the end of study, serious adverse events will continue to be reported as detailed in Attachments 11 and 12. For subjects who have received subsequent treatment with therapeutic intent for multiple myeloma during the adverse event reporting period, only adverse events that are considered to be possibly, probably, or definitely related to daratumumab need to be reported. Serious adverse events, including those spontaneously reported to the investigator within 30 days after the last dose of study treatment, must be reported using the Adverse Event Form. The sponsor will evaluate any safety information that is spontaneously reported by an investigator beyond the time frame specified in the protocol.

Expected progression of disease should not be considered an AE (or SAE). However, if determined by the investigator to be more likely related to the study treatment than the underlying disease, the clinical signs or symptoms of progression and the possibility that the study treatment is enhancing

disease progression, should be reported per the usual reporting requirements (see Section 12.1). Death should not be recorded as an adverse event or serious adverse event, but as the outcome of an adverse event. The adverse event that resulted in the death should be reported as a serious adverse event. All events that meet the definition of a serious adverse event will be reported as serious adverse events, regardless of whether they are protocol-specific assessments. Anticipated events will be recorded and reported as described in Attachment 10. Anticipated events will be no longer be reported after the final CSR analysis.

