2.3. Study Treatment and Study Drug

In this study, study treatment refers to lenalidomide, dexamethasone, and/or daratumumab. Study drug refers to daratumumab.

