2.9. Analysis Sets

The following analysis sets are defined.

- Intent-to-treat (ITT): defined as subjects who have been randomly assigned to the DRd or Rd group. Analyses of demographics, baseline characteristics and efficacy endpoints will be primarily analyzed based on this population.
- Safety population: defined as subjects who have received at least 1 administration of any study treatment (partial or complete). This population will be used for all safety analyses. The safety analyses grouping will be according to treatment actually received.
- Response-evaluable: defined as subjects who have a confirmed diagnosis of multiple
 myeloma and measurable disease at baseline or screening visit. In addition, subjects must
 have received at least one administration of study treatment and have adequate postbaseline disease assessments. Measurable disease is defined as follows:
 - IgG myeloma: Serum monoclonal paraprotein (M-protein) level ≥1.0 g/dL or urine M-protein level ≥200 mg/24 hours; or
 - IgA, IgD, IgE or IgM multiple myeloma: serum M-protein level ≥0.5 g/dL or urine M-protein level ≥200 mg/24 hours; or
 - Light chain multiple myeloma without measurable disease in serum or urine: Serum immunoglobulin free light chain (FLC) level ≥10 mg/dL and abnormal serum immunoglobulin kappa lambda free light chain ratio.

This population will be used as sensitivity analyses for selective response-related secondary endpoints such as CR or better rate.

- Per-protocol (PP) population: defined as subjects who are randomized and meet all eligibility criteria.
- Pharmacokinetics-evaluable: is defined as subjects assigned to DRd group who received at least 1 administration of daratumumab and have at least 1 pharmacokinetic sample concentration value after the first infusion. All pharmacokinetics analyses are based on the pharmacokinetic evaluable population.
- Immune response-evaluable: is defined as subjects assigned to DRd group who have at least 1 immunogenicity sample obtained after their first daratumumab administration.
- Molecular genetic evaluable: defined as subjects who meet one of the following biomarker criteria for risk assessment based on the next generation sequencing (NGS) data:
 - Standard risk: subjects that are negative (=molecular aberration absent) for all del17p, t(14;16), t(4;14).
 - High risk: subjects that are positive (=molecular aberration present) for any of del17p, t(14;16), t(4;14).

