2.11. Other General Definitions

2.11.1. Treatment Emergent Adverse Events

Treatment emergent adverse events (TEAEs) are defined as any AE with onset date and time on or after that of the first dose of study drug infusion through 30 days after the last dose of study drug or the day prior to start of subsequent therapy, whichever is earlier; or any AE that is considered related to (probably, possibly, or very likely) study drug regardless of the start date of the event. AEs with missing or partial onset date and time will be considered as treatment-emergent unless the onset date and time of an AE can be determined as earlier than that of the first dose, or later than 30 days after last dose.

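### Read literally, the SAP would count serious daratumumab-related events after crossover as Rd treatment-emergent events in the final CSR safety update

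*SAP*

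**What the plan says.** SAP 5.1 defines a treatment-emergent adverse event (TEAE) first by time: from the first study treatment to 30 days after the last, or to the day before subsequent antimyeloma therapy if that is earlier. It then adds a second route with no time limit: "any AE that is considered drug-related (very likely, probably, or possibly related) regardless of the start date of the event". SAP 2.11.1 repeats that route in other terms: "any AE that is considered related to (probably, possibly, or very likely) study drug regardless of the start date of the event". SAP 2.3 says "Study drug refers to daratumumab", and lists lenalidomide, dexamethasone and/or daratumumab as study treatment without tying the list to an arm.

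On collection, the opening sentence of SAP 5.1 stops AE reporting at several points, one of them "until the subject starts subsequent antimyeloma therapy, whichever occurs first". Protocol 8.4, which came in with Amendment 5, lets Arm A subjects receive sponsor-supplied daratumumab after progression. These subjects "will remain in the long-term survival follow-up phase of the study", and "Serious adverse events must be reported for these subjects until 30 days after daratumumab is discontinued". Protocol 12.3.1 adds that, for subjects who have started another myeloma therapy within the AE reporting period, "only adverse events that are considered to be possibly, probably, or definitely related to daratumumab need to be reported".

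On grouping, SAP 2.9 says "The safety analyses grouping will be according to treatment actually received". It does not mention crossover.

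**The concern.** The relatedness route is there to catch late toxicity of the assigned regimen. Once Rd subjects can receive daratumumab from the sponsor, the same wording also catches toxicity of the experimental drug given as a later line. The plan has no exclusion, flag or separate table for such events. Protocol 11.3 recognises that crossover may confound overall survival, but neither document makes the matching point for safety.

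What is at stake is the comparison of related TEAEs, related SAEs and TEAE deaths in the final CSR, which updates safety about 5 years after the last randomisation. Events caused by daratumumab would sit in the column meant to show what happens without it. Taken alone, that would understate the toxicity added by daratumumab.

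**Working it through.** The documents state no figure on this point, so there is none to reproduce. The check is a trace through the definitions, then the dates, then an illustrative size.

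**1. Trace.** Take an Rd subject who progresses, starts sponsor-supplied daratumumab and has a serious event judged related to it.

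- Timed window (SAP 5.1): closed the day before subsequent therapy, so the event does not qualify this way.
- Relatedness route: SAP 5.1 asks only that the event be drug-related and names no drug. SAP 2.11.1 asks that it be related to study drug, which SAP 2.3 defines as daratumumab. The event qualifies under both.
- Related-event tables (SAP 5.1.4 and 5.1.5): these use relationship to study treatment. The list in SAP 2.3 includes daratumumab with no condition on arm, so the event fits.
- Fatal case (SAP 5.2.1): counted if the AE CRF page shows outcome death or grade 5.
- Column (SAP 2.9): not settled for crossover. The natural reading keeps the subject under Rd; the text does not rule out a move to DRd.
- Collection: Protocol 8.4 requires the SAE. Protocol 12.3.1 sends SAEs to the adverse event form and requires all AEs, whatever their seriousness, to be recorded in the eCRF. Attachments 11 and 12 limit what enters the clinical database in later phases; Section 8.4 sets no such limit.

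**2. Dates.**

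- Primary clinical cut-off (Protocol 3.1): 24 September 2018.
- SAP v2.0, written for INT-4: 3 October 2018.
- Amendment 5: 15 January 2019, which is 113 days after the cut-off and 104 days after the SAP.

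Sponsor-provided crossover therefore contributes nothing to the primary safety tables. The exposed analysis is the final CSR update.

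**3. Size.** Points added to Rd = crossover share × rate of serious daratumumab-related events among those who cross over. Subjects added = 365 × that product. The 365 is the planned Rd arm (Protocol 3.1); both other inputs are assumptions.

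| Crossover share | Event rate | Points added | Subjects of 365 |
|---|---|---|---|
| 10% | 5% | 0.5 | 1.8 |
| 10% | 10% | 1.0 | 3.7 |
| 30% | 5% | 1.5 | 5.5 |
| 30% | 10% | 3.0 | 11.0 |

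With wider assumptions (share 10-50%, rate 1-10%) the range is 0.1 point (0.4 subjects) to 5.0 points (about 18 subjects). These are upper bounds for the assumptions used: a subject who already has a related SAE is not counted twice, and every such event is taken to reach the TEAE tables.

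**The case against.** Five points weigh against the concern.

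- **General collection stops.** A reader might infer that every daratumumab reaction after crossover counts against Rd. The documents do not support that. SAP 5.1 ends general AE reporting at subsequent therapy, and post-progression daratumumab is a subsequent therapy. Apart from the narrow sentence in Protocol 12.3.1, only SAEs are required. This stands and limits the point to serious events.
- **Entry into the TEAE data is not explicit.** Protocol 9.1.5 and 9.1.7 list what is collected after progression and do not mention adverse events. Protocol 8.4 names no form, and 12.3.2 sends SAEs on a separate form. Entry into the AE data is the default under 12.3.1, but it sits uneasily with those lists. This stands as uncertainty.
- **The intended meaning may be narrower.** SAP 2.4 dates Rd treatment by lenalidomide and dexamethasone only, and Protocol 11.9 describes the AE analysis as covering events that begin in the treatment phase. On that view a reaction to next-line daratumumab is not an Rd event. But SAP 2.4 governs dosing dates, not relatedness, and the SAP's undated route is wider than Protocol 11.9. This supports making the restriction explicit.
- **The primary analysis came first.** The dates above confirm this, and it stands in full.
- **Another rule may pull the other way.** After next-line therapy starts, 12.3.1 keeps daratumumab-related events only, which tends to add late related events to DRd. That window is narrow. The net direction of the two effects cannot be settled from the documents, and they should not be assumed to cancel.

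**Conclusion.** The gap is real and limited. As written, the TEAE definition has no stop at subsequent therapy for related events and was not revised for Amendment 5. A serious daratumumab-related event in a crossover Rd subject therefore meets it and would appear under Rd in the final CSR safety update.

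A reader might go further and conclude that the Rd safety column is already contaminated. The documents do not show that. They give no number crossing over and no rate of serious related events, and they do not state outright that SAEs reported under Protocol 8.4 enter the AE data behind the tables. The 0.5-3.0 points rest wholly on the assumed 10-30% crossover and 5-10% event rate. Even a few such events matter, because they would be attributed to a comparator randomised not to receive the drug.

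**What to change.** - In SAP 5.1 and 2.11.1, limit the undated route to events attributed to a component of the subject's assigned study treatment: lenalidomide or dexamethasone for Rd; these or daratumumab for DRd.
- Keep late lenalidomide- or dexamethasone-related events in both arms.
- Report Arm A SAEs attributed only to post-progression daratumumab in a separate crossover table.
- In SAP 2.9, state that post-progression daratumumab does not change the safety treatment group.

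The cost is one extra table and one programming condition. The condition needs attribution by component. The documents do not say whether the eCRF holds that, but start dates of subsequent therapy are collected (Protocol 8.4) and would identify the Arm A SAEs to review.

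Two broader remedies should be avoided. Excluding every Arm A event after crossover would drop late lenalidomide-related serious events, including second primary malignancies, in one arm only. Rewording Protocol 12.3.1 now could not recover events that were never collected.

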5.1.1. Overview of TEAEs

An overview of TEAEs reported through the study will be provided for each treatment group. The overview will include summaries of subjects with TEAEs, with TEAEs related to study treatment, with TEAEs of maximum toxicity grade of 1 to 5, SAEs, TEAEs leading to discontinuation of all study treatment.

5.1.2. All TEAEs

- Incidence of TEAEs by MedDRA SOC and preferred term.
- Most commonly reported (>10%) TEAE by MedDRA SOC and preferred term.

5.1.3. Toxicity Grade 3 or 4 TEAEs

- Incidence of toxicity Grade 3 or 4 TEAEs, by MedDRA SOC and preferred term
- List of subjects with any toxicity Grade 3 or 4 TEAEs
- Most commonly reported (>5%) Grade 3 or 4 TEAE by MedDRA SOC and preferred term

5.1.4. Study Treatment-Related TEAEs

- Incidence of TEAEs considered by the investigator to be related to study treatment, by MedDRA SOC, preferred term and relationship to study treatment
- Incidence of TEAEs with toxicity Grade 3 or 4 considered by the investigator to be related to study treatment, by MedDRA SOC and preferred term and relationship to study treatment

5.1.5. Serious Adverse Events (SAEs)

- Incidence of treatment-emergent SAEs, by MedDRA SOC and preferred term
- Incidence of treatment-emergent SAEs considered by the investigator to be related to study treatment, by MedDRA SOC, preferred term and relationship to treatment
- Most commonly reported (>2%) SAEs by MedDRA SOC and preferred term
- List of subjects with any treatment-emergent SAEs

5.1.6. TEAEs Leading to Dose Modifications

Incidence of TEAEs leading to dose modifications will be summarized by MedDRA SOC and preferred term. The summaries will be presented by all grades and Grade 3 or 4 for each treatment. This table will include TEAEs leading to cycle delays or dose modification of at least 1 of the study treatments, the dose modifications include dose delay within the cycle, dose reduced (not applicable to daratumumab), dose re-escalated per protocol (not applicable to daratumumab), or dose skipped.

5.1.7. TEAEs Leading to Discontinuation of Any Study Treatment

A summary of number of subjects who discontinued any study treatment because of 1 or more TEAEs by MedDRA system-organ class and preferred term will be provided. The summaries will be presented by all grades and Grade 3 or 4 for each treatment group. The AEs leading to discontinuation of any study treatment are based on AEs recorded in the AE CRF page with an action taken of drug withdrawal for any study treatment.

A listing of subjects who discontinued any study treatment because of TEAEs will be provided

5.1.8. TEAEs Leading to Discontinuation of All Study Treatment

A summary of number of subjects who discontinued all study treatment because of 1 or more TEAEs by MedDRA system-organ class and preferred term will be provided. A listing of subjects who discontinued all study treatment because of TEAEs will be provided, this listing includes TEAEs leading to discontinuation of all study treatment for those subjects indicated as having discontinued study treatment due to an adverse event on the end of treatment CRF page.

5.2. Deaths

5.2.1. Death Due to TEAEs

The number of subjects who died due to treatment-emergent adverse events will be summarized by preferred term and relationship to study treatment for each treatment group. The TEAEs included in this table are AEs with outcome death or toxicity grade of 5 recorded in the AE CRF page.

A listing of subjects who died due to treatment-emergent adverse events will be provided.

5.2.2. Deaths

A summary of all deaths and cause of death will be tabulated overall and by treatment group. Specifically, the number of subjects who died during the study will be summarized for the ITT population. The primary cause of death collected on the death information CRF page will be reported. If the primary cause of death is AE, the number of subjects who have related AE and unrelated AE will be further reported.

Subjects who died within 30 days of last study treatment dose and within 60 days of first study treatment dose, respectively, based on the safety population.

A listing of all deaths will be provided.

5.2.3. Adverse Events by Subgroups

The following subgroup analysis of adverse events will be performed based on subgroups specified in Section 2.10:

- Overview of TEAEs
- All TEAEs
- Toxicity Grade 3 or 4 TEAEs
- SAEs.

5.3. Adverse Events of Clinical Interest

The adverse events of clinical interest would be focus on below items (detail would be defined on the DPS or below sections),

- IRR
- Infections and Infestations
 - Opportunistic infections
 - Virus infections
- Hemorrhage events
- Interferences for blood typing
- Tumor lysis syndromes
- Intravascular hemolysis
- Cytopenia
 - Neutropenia events
 - Thrombocytopenia events
 - Anaemia
 - Lymphopenia
- Second Primary Malignancies

5.3.1. Infusion-Related Reactions (IRR)

Subjects with any IRR associated with daratumumab administration will be summarized by MedDRA system-organ class and preferred term. The summaries will be presented by all grades, Grade 3, 4, and 5. In addition, the total number of subjects with IRR in more than 1 infusion will be reported. Additionally, the timing of IRR associated with daratumumab administration will be evaluated through a summary of IRR by event onset time.

A listing of subjects with Grade 3 or higher treatment-emergent infusion-related reactions associate with daratumumab administration will be provided. In addition, subjects with treatment-emergent infusion-related reactions results in discontinuation of daratumumab will be listed.

